3.2 Clinical Event Description and CEC Adjudication

Three types of events are defined in the sections below. All clinical events will be adjudicated by a Clinical Events Committee (CEC) consisting of a blinded panel of independent experts. Once the CEC adjudicates the Clinical Events, and per defined criteria in section 3.2.2, all Type I ST episodes will be classified as either False Positive or True Positive events. In addition, any Clinical Event that was not associated with a Type I ST episode detection will be classified as either False Negative or True Negative.

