3.2.3 Classification of Events

True Positive (TP): A Type I ST episode detection that occurs up to 72 hours prior to an ACS Event.

False Positive (FP): A Type I ST episode detection that occurs more than 72 hours prior to an ACS Event or that occurs in the absence of a true ACS Event.

True Negative (TN): Absence of a Type I ST episode detection during a Non Event.

False Negative (FN): Absence of a Type I ST episode detection within 72 hours prior to an ACS Event.

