3.3 Patient Selection

3.3.1 Inclusion Criteria

Eligible patients will meet **all** of the following:

1. Have an indication for an ICD implantation or pulse generator change
2. Have documented coronary artery disease. Documented coronary artery disease is defined as having at least one of the following present a) evidence of a prior MI on ECG and/or cardiac enzymes, b) prior revascularization (by coronary artery bypass grafting or percutaneous coronary intervention) c) angina and/or ST-T wave abnormalities indicative of ischemia on exercise stress test, nuclear stress test, or echo stress test, or d) coronary artery disease diagnosed by coronary angiography.
3. Willing and able to comply with protocol requirements, including keeping all required visits
4. Willing to participate in the study and able to sign an IRB approved informed consent form
5. Willing and capable of using Merlin@home.
6. Be at least 18 years of age when enrolled in the study

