An empirical analysis will be provided for the proportion of patients experiencing false positive events using the estimator described in the Primary Analysis section. The standard error of this empirical estimate will be calculated as the standard deviation of a bootstrap distribution. The bootstrap distribution will be constructed using 1,000 bootstrap resamples. Each bootstrap resample will be performed at the patient level, and each resample will have a total sample size equal to the total number of evaluable patients. A two-sided 95% bootstrap confidence interval will be provided.

Subgroup Analysis

The analysis of the primary safety endpoint will be performed on the following the subgroups of patients

- Coronary artery disease patients with cardiomyopathy
- Coronary artery disease patients without cardiomyopathy
- Patients with abnormal baseline ECGs, for each of six abnormal subgroup categories
- Patients with normal baseline ECGs
- Patients with arrhythmias
- Gender
- Patients alerted via Merlin.net and patients alerted via device Patient Notifier

Sample Size

optimize ST feature parameters. The analysis with a 3-month run-in period

[REDACTED]

[REDACTED]

[REDACTED]

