An empirical analysis will be provided for the sensitivity of the ST Monitoring Feature to detect clinical events using the estimator described in the Primary Analysis section. The standard error of this empirical estimate will be calculated as the standard deviation of a bootstrap distribution. The bootstrap distribution will be constructed using 1,000 bootstrap resamples. Each bootstrap resample will be performed at the patient level (in order to preserve the correlation structure of multiple events within one patient, if the occurs), and each resample will have a total sample size equal to the total number of evaluable patients. A two-sided 95% bootstrap confidence interval will be provided.

Subgroup Analysis

The analysis of the primary efficacy endpoint will be performed on the following subgroups of patients

- Coronary artery disease patients with cardiomyopathy
- Coronary artery disease patients without cardiomyopathy
- Patients with abnormal baseline ECGs, for each of six abnormal subgroup categories
- Patients with normal baseline ECGs
- Patients with arrhythmias
- Gender
- Patients alerted via Merlin.net and patients alerted via device Patient Notifier

Sample Size

[REDACTED]

The patients to be enrolled in the Analyze ST IDE Study are similar to those

[REDACTED]

the total number of patients required to be enrolled is 5,228.

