4.7.6 Response Rates to Patient Notifier and Merlin.net Type I ST Episode Detections

The response rates to Type I ST Episode notifications received through the Patient Notifier and through Merlin.net will be presented.

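### The subgroup by alert route is undefined and, as worded, selects patients on a post-baseline detection, so FP%, FPR and sensitivity in it are biased upward and cannot be read against the goals

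*Protocol*

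**What the plan says.** The Protocol and SAP carry the same text on this point. Section 4.3.2 states "The analysis of the primary safety endpoint will be performed on the following the subgroups of patients", and the last item in the list is "Patients alerted via Merlin.net and patients alerted via device Patient Notifier". The same item appears in the lists of 4.3.1 (preliminary safety assessment), 4.3.3 (FPR) and 4.4.1, where "The analysis of the primary efficacy endpoint will be performed on the following subgroups of patients".

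Neither document says what makes a patient alerted, or where a patient with no alert, or with alerts by both routes, belongs. The nearest description is section 4.7.6: "The response rates to Type I ST Episode notifications received through the Patient Notifier and through Merlin.net will be presented". An alert there is a notification of a Type I ST episode. Section 3.2 adds that "all Type I ST episodes will be classified as either False Positive or True Positive events".

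Two further provisions matter. The patient groups in 4.3.2, 4.3.3 and 4.4.1, and the inclusion rule in 4.3.1, all require the Patient Notifier to be on. Section 3.3.1 requires every patient to be "Willing and capable of using Merlin@home".

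**The concern.** The other listed subgroups are mostly patient characteristics. This one depends on something that happens during follow-up, and that something is the component from which the endpoints are built. A patient who never has a detection cannot be alerted. Such patients are the bulk of the FP-free denominator in 4.3.2 and of the patient-years in 4.3.3. For 4.4.1, a patient whose ACS event was missed stays in the subgroup only if another episode produced an alert.

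Reading the item as the route programmed, rather than the route that fired, does not repair it. With the Notifier on in every analysed patient, the Notifier group is the whole analysis population.

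At stake is the reading of planned outputs in a pivotal study. The same data could appear to show a serious false-alarm problem and very good sensitivity, both produced by selection.

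**Working it through.** The documents give no figure for this subgroup, and the planning values for FP% and sensitivity are not visible, so there is nothing to reproduce. The check shows what the conditioning does over a range of assumed values.

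**Inputs from the documents**
- Enrolment 5,228 and at least 41 clinical events (section 4.5 of the Protocol); both used as planning values.
- FP% = patients with a false positive / evaluable patients, goal below 15% (4.3.2).
- Sensitivity = TP events / ACS events, goal above 50%, judged on the Wilson lower bound (4.4.1).
- FPR = false positives / patient-years, goal below 1.9 (4.3.3).
- A detection counts as a false positive when no ACS event follows it within 72 hours; a false negative is "Absence of a Type I ST episode detection within 72 hours prior to an ACS Event" (3.2.3).

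**Assumptions not in the documents**
- One ACS event per patient.
- Every detection produces an alert.
- FP status is independent of ACS status.
- Both routes are taken together, because the split between them is unknown.

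Let f be the share of all patients with a false positive, s the overall sensitivity, and t = 41s/5,228 the share with a true positive.

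**FP% among alerted patients.** Alerted patients have a false positive, or true positives only, so FP% = f / [f + t(1 − f)].
- f = 14%, s = 0.50: t = 0.00392, and 0.14 / (0.14 + 0.00337) = 97.6%.
- f = 10%, s = 0.75: t = 0.00588, and 0.10 / (0.10 + 0.00529) = 95.0%.

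| Overall FP% | Alerted FP%, s = 0.75 to 0.50 |
|---|---|
| 14% | 96.5-97.6% |
| 10% | 95.0-96.6% |
| 5% | 89.9-93.1% |
| 2% | 77.6-83.9% |
| 1% | 63.2-72.0% |

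The overall test passes with up to 733/5,228 = 14.0%, so a device that meets the safety goal can show about 97% here. For alerted FP% to fall to 15%, patients with true positives only would have to number 0.85/0.15 = 5.67 times the FP patients, which is 28% of all patients at f = 5%. The planned event count allows at most 41/5,228 = 0.8%.

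**Sensitivity among alerted patients.** Missed events stay in only when the patient also had a false positive, so sensitivity = s / [s + (1 − s)f].
- s = 0.50, f = 14%: 0.50 / (0.50 + 0.07) = 87.7%.
- s = 0.50, f = 5%: 0.50 / (0.50 + 0.025) = 95.2%.
- s = 0.75, f = 14%: 0.75 / (0.75 + 0.035) = 95.5%.
- s = 0.30, f = 14%: 0.30 / (0.30 + 0.098) = 75.4%.

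In 40,000 simulated trials at s = 0.50 (the null boundary) and f = 14%, the Wilson lower bound in the subgroup exceeded 50% in 98.6%, against about 3% for the whole population. At s = 0.40 and f = 14%, the subgroup bound exceeded 50% in 88%.

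**FPR.** All false positives stay while detection-free patient-years leave, so the rate must rise. Suppose each patient has one year of follow-up and each FP patient one counted event. At f = 14% and s = 0.50 the overall rate is 0.14, and the subgroup rate is 0.14/0.1434 = 0.98 per patient-year. That is about seven times higher, but below 1.9.

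**The case against.** A reader might infer that FP% and sensitivity in this subgroup are close to 100% by construction. The documents do not support that. FP% among alerted patients is in effect one minus a patient-level positive predictive value. It is very high when the overall FP% is near the 15% goal, but 63-72% when the overall FP% is 1%. Sensitivity is not forced to 100%, because a false negative is judged per ACS event over 72 hours. A patient alerted at another time can therefore still contribute a missed event.

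The inputs also favour large figures. The 5,228 is enrolment, while the endpoint uses evaluable patients; with an assumed 2,500 evaluable, alerted FP% at f = 5% is 81.1-86.5%. The 41 events are a minimum, and more true positives would lower FP%. If patients with missed events have more false positives than others, sensitivity is inflated less. All of this stands as to size. The direction does not change: with every detection alerting and one ACS event per patient, removing patients without detections cannot lower FP% or sensitivity.

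A reader might also infer that the subgroup would fail the 1.9 goal. That is not shown. Section 4.3.3 counts at most one false positive per follow-up period and two per patient, so failure would need second false positives to be common or early.

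Two points on interpretation remain. Section 4.7.10 refers to a separate investigational protocol, which might define an alert. And being able to use Merlin@home does not prove that Merlin.net alerting was enabled for everyone, so a programmed-route reading is unlikely but not excluded. Even then the two groups overlap, and a definition is still needed.

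Finally, no success claim rests on subgroups, and in 4.3.1 the split has a use: complications and medical care that follow an alert can arise only in alerted patients. This limits the consequence and narrows the fix.

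**Conclusion.** The point holds as a defect in a planned subgroup analysis, of minor consequence. The item is undefined and, on its natural reading, conditions on a post-baseline detection. FP%, FPR and sensitivity in it are biased upward and say nothing about the 15%, 1.9 and 50% goals.

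The size depends on the overall FP%, which the documents do not show. With s = 0.50-0.75 and the stated assumptions, alerted FP% is about 95-98% for an overall FP% of 10-14%, and about 63-93% for 1-5%. A true sensitivity of 50% appears as about 88% at an overall FP% of 14%, and about 95% at 5%. Only the direction is established for the FPR. The primary tests use the whole analysis population and are not affected.

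**What to change.** - Remove the item from the subgroup lists in 4.3.2, 4.3.3 and 4.4.1, and from the FP-proportion and sensitivity summaries in 4.3.1.
- Compare alert routes among detections only: response rates, as already planned in 4.7.6, and the positive predictive value of 4.7.4 reported by route.
- Keep the route split in 4.3.1 as description only, for complications and medical care following alerts. State what counts as an alert and how patients alerted by both routes are shown.

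Redefining the subgroup by the route enabled at Baseline is not a ready substitute, because the Notifier is on in everyone analysed.

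The cost is a wording change plus one added breakdown of the predictive value. The downside is that patient-level endpoint results by alert route are lost.

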4.3.3 Secondary Safety Endpoint

The ST Monitoring Feature will be evaluated by the False Positive Rate (FPR). The False Positive Rate is calculated as the number of false positives per patient-year of follow-up. A False Positive occurs when there is a Type I ST episode that is not followed by a clinical event within 72 hours. Only ST segment shift events that occur beyond the baseline visit will be included in this analysis.

$$\text{FPR} = \frac{\text{\#of false positive events}}{\text{patient years of follow-up}}$$

The hypothesis is formally expressed as follows:

H₀: Expected FPR ≥ 1.9 per patient-year of follow-up

H_a: Expected FPR < 1.9 per patient-year of follow-up

The desired outcome is to demonstrate that the False Positive Rate is less than 1.9 events per patient-year. The null hypothesis will be rejected at the 2.5% significance level if the 97.5% upper confidence limit (UCL) for the expected FPR is less than 1.9 per patient-year of follow-up.

Statistical Analysis Plan

Patient Group

All enrolled patients who have a successful implant or system revision and have completed the Baseline visit with the ST Monitoring Feature and Patient Notifier programmed ON will be included in this endpoint.

Further, the analysis population for the secondary safety endpoint will be those subjects with the Fortify® ST (upgraded), Fortify Assura® ST and Ellipse® ST devices. The data from subjects with a Fortify® ST prior to being upgraded will not be included in this analysis.

Analysis

Primary Analysis

The expected FPR will be estimated by the observed FPR. To avoid imbalance in the number of false positives that each patient with false positives contributes, the maximum number of false positives from a patient that will be counted toward meeting the requirement on the number of false positives will be two. In addition, for a single follow up period (i.e. one interrogation and device evaluation to the next), if multiple false positive events occur, only one event will be counted toward the analysis. This will prevent multiple false positives that occur before the physician has the opportunity to evaluate the patient and reprogram the device from contributing to an imbalance in the data. For any patients with more than two false positives their follow up time will be truncated to the date of the second false positive.

The analysis will be carried out where only those false positives counted toward meeting the requirement of number of false positives are included. That is, if a patient has experienced more than two false positives, only the first two false positives of that patient will be included.

The 97.5% upper confidence limit for the expected FPR will be calculated based on the confidence interval calculation of a Poisson rate using the exact method (Ulm, 1990)⁶. The null hypothesis will be rejected at the 2.5% significance level if the 97.5% upper confidence limit is less than 1.9 per patient-year.

Additional Analyses

Empirical analyses will be provided for the false positive rate using

1. the estimator described in the Primary Analysis section, and
2. the estimator that uses all false positive events.

The standard error of these empirical estimators will be calculated as the standard deviation of their bootstrap distributions. The bootstrap distributions will be

Statistical Analysis Plan

constructed using 1,000 bootstrap resamples. Each bootstrap resample will be performed at the patient level (in order to preserve the correlation structure between events with a given patient), and each resample will have a total sample size equal to the total number of evaluable patients. The bootstrap distributions will be used to estimate two-sided 95% bootstrap confidence intervals.

Subgroup Analysis

The analysis of the secondary safety endpoint will be performed on the following subgroups of patients

- Coronary artery disease patients with cardiomyopathy
- Coronary artery disease patients without cardiomyopathy
- Patients with abnormal baseline ECGs, for each of six abnormal subgroup categories
- Patients with normal baseline ECGs
- Patients with arrhythmias
- Gender
- Patients alerted via Merlin.net and patients alerted via device Patient Notifier

[figure not shown]
Sample Size

[REDACTED]

[REDACTED]

[REDACTED]

[REDACTED]

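### The secondary false positive rate counts at most one false positive per evaluation interval but leaves the blocked time in patient-years, so the rate reads low and the 2.5% level against 1.9 does not hold

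*Protocol*

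**What the plan says.** Section 4.3.3 reads the same in the Protocol and the SAP. The definition is unqualified: "The False Positive Rate is calculated as the number of false positives per patient-year of follow-up". So is the aim: "The desired outcome is to demonstrate that the False Positive Rate is less than 1.9 events per patient-year". The null hypothesis is an expected FPR of at least 1.9.

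The primary analysis then limits the numerator in two ways:

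- Within one follow-up period, meaning the interval between successive interrogations with device evaluation, "if multiple false positive events occur, only one event will be counted toward the analysis". The reason given is that the physician has not yet been able to evaluate the patient and reprogram the device.
- No patient contributes more than two false positives.

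Only one adjustment to patient-years is stated: patients with more than two false positives have their follow-up cut at the second.

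The upper limit is "calculated based on the confidence interval calculation of a Poisson rate using the exact method", and the decision rule is: "The null hypothesis will be rejected at the 2.5% significance level if the 97.5% upper confidence limit is less than 1.9 per patient-year".

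Under Additional Analyses, 4.3.3 also plans an estimator that uses all false positives, with a two-sided 95% bootstrap interval from 1,000 patient-level resamples. No decision rests on it.

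**The concern.** A Poisson limit for a rate needs a denominator made up of time in which a countable event could occur. Once a false positive has been counted, nothing further can count until the next device evaluation, yet nothing in 4.3.3 takes that time out. Events leave the numerator while their time stays in the denominator. The error can only lower the rate, which favours the device.

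At stake is a formal safety hypothesis. A feature whose true rate is at the unacceptable boundary could be declared below it far more often than the stated 2.5% of the time.

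**Working it through.** **Inputs from the documents (4.3.3 unless noted).** Margin 1.9 per patient-year; one-sided level 2.5%; exact Poisson limit; at most one counted false positive per interval; at most two per patient; truncation only above two; 12 months of follow-up (3.1).

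**Assumptions.** The interval length is not given and the sample size text is redacted. Intervals from one week to six months and trials of 100 or 500 patients, one year each, are therefore illustrative. The rate is constant unless stated.

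**Step 1: the stated level, all events counted.** Upper limit = χ²(0.975; 2(x+1)) / (2 × patient-years). At 500 patient-years the largest passing count is 889. With a true rate of 1.9 the expected count is 950, and P(X ≤ 889) = 0.024. At 50, 100 and 1,000 patient-years the level is 0.020, 0.021 and 0.024. So 2.5% holds when every false positive counts.

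**Step 2: the interval rule alone (no cap).**

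If the evaluation follows a counted false positive after a lag L (years), the long-run counted rate is 1.9 / (1 + 1.9L):

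| Lag | Counted rate | Expected count, 500 patient-years | Simulated false pass, n = 500 |
|---|---|---|---|
| 7 days | 1.9/1.036 = 1.83 | about 917 | 16–21% |
| 14 days | 1.9/1.073 = 1.77 | about 885 | about 54% |
| 30 days | 1.9/1.156 = 1.64 | about 822 | about 99% |

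At 14 days the expected count is already below the passing threshold of 889, so about half of such trials pass.

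If evaluations occur only on a fixed schedule every T years, the counted rate is (1 − exp(−1.9T)) / T:

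| Schedule | Counted rate | False pass, n = 100 / 500 |
|---|---|---|
| 1 week | 1.87 | 0.02 / 0.06 |
| 1 month | 1.76 | 0.14 / 0.67 |
| 3 months | 0.378/0.25 = 1.51 | 0.87 / 1.00 |
| 6 months | 0.613/0.5 = 1.23 | 1.00 / 1.00 |

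The weekly schedule is milder than the 7-day lag because the average wait is about half a week.

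Solving the schedule formula for a counted rate of 1.9 gives a true rate of −ln(1 − 1.9T)/T: 1.94 (weekly), 2.07 (monthly), 2.58 (3-monthly) and 5.99 (6-monthly).

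**Step 3: the cap of two alone.** With N Poisson with mean 1.9 over one year:

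- P(1) = 0.284, P(2) = 0.270, P(≥2) = 0.566, P(≤2) = 0.704, P(≥4) = 0.125.
- Counted events per patient: 0.284 + 2 × 0.566 = 1.417.
- Patient-years as written: 0.704 + (2/1.9) × 0.125 = 0.836. The second term is the time to the second event in patients with three or more.
- Rate: 1.417/0.836 = 1.695.

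The shortfall comes from patients with exactly two false positives. They keep all their time after the second, worth 0.270 × 1/3 = 0.090 patient-years. Ending time at the second event for them as well gives 1.417/0.746 = 1.90.

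**Step 4: both rules as written.** The text does not say whether truncation refers to raw or counted false positives, so three readings were simulated. On fixed schedules the rate is about 1.68 (weekly), 1.62–1.64 (monthly), 1.46–1.52 (3-monthly) and 1.23–1.32 (6-monthly). With 100 patients, the false-pass chance is 0.27–0.29, 0.38–0.46, 0.79–0.95 and about 1.00.

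**Step 5: what restores the level.**

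- Removing only the blocked interval time, with the cap left as written: the rate is still about 1.7. At n = 500 the false-pass chance is roughly 70–90% for 7- and 14-day lags, and lower but still far above 2.5% at 30 days.
- Also ending time at the second counted false positive for everyone who reaches two: the rate is 1.89–1.91 and the level about 2–3%, under a constant rate.
- If rates differ between patients (assumed gamma, shape 1, mean 1.9), that fuller correction still gives only 1.18–1.40. Counting all events restores about 1.9, but the Poisson limit then has a level of about 0.11–0.18. This is why a patient-level bootstrap limit is needed.

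**The case against.** **The rule is deliberate.** It keeps a burst of detections before reprogramming from dominating. That reason stands, and the rule can stay in a supportive analysis. It does not justify testing the reduced count against a margin defined on all false positives. If the sponsor intended an interval-limited rate, the hypothesis and the 1.9 would have to say so. The visible text does not, and the derivation of 1.9 cannot be checked because the sample size text is redacted.

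**Alerts may bring patients in quickly.** Patients are alerted by the Patient Notifier or Merlin.net, and response to alerts is tracked (4.7.6). With evaluation within about a week, the interval rule alone costs little (1.8% of the rate on a weekly schedule). This stands. The 3- and 6-monthly figures assume that no alert prompts an evaluation, so they are outer bounds and not expectations. But 4.3.3 sets no maximum interval.

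**A device at 1.9 would fail the primary safety endpoint anyway.** Under a constant rate, 1 − exp(−1.9) = 85% of patients would have a false positive, against the 15% goal in 4.3.2. This limits the practical harm, but only when rates are similar across patients. Suppose the false positives fall in 15% of patients, with one year planned for each. The capped count is at most 2 × 0.15 = 0.30 per patient over at least 0.85 patient-years, or 0.35 per patient-year. The reduced-count test then passes whatever the total burden in those patients.

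**A stronger reading that the documents do not support.** Since "Only ST segment shift events that occur beyond the baseline visit will be included in this analysis" limits the numerator and 4.3.3 gives no start date for patient-years, a reader might infer that run-in time inflates the denominator. That rests on silence alone. The population has completed Baseline, 3.1 places the 12 months after the run-in, and 4.3.1 starts follow-up at Baseline or at the upgrade visit.

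**Conclusion.** The point holds. As written, the primary FPR analysis is biased low whenever false positives can recur within an interval, and its 2.5% level does not hold for the hypothesis as stated. That the blocked time stays in the denominator follows from the FPR definition and the single truncation rule; no sentence says so in words.

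The direction is the same under every reading tried. The size is not fixed by the documents. It runs from almost nothing (weekly evaluations, 100 patients, interval rule alone) to a near-certain false pass (30-day lag, 500 patients). All these figures assume a true rate of 1.9 and one year per patient.

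A reader might infer that stopping the clock after each counted false positive would repair the test. It would not, because the cap with truncation only above two by itself lowers the rate to about 1.7 at a true 1.9. The all-events bootstrap would expose the problem, but it carries no decision. This should be corrected. It affects a secondary endpoint, so it does not undermine the primary safety or efficacy tests.

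**What to change.** In 4.3.3 of both documents, base the 1.9 decision on the rate that uses all false positives over full follow-up. Reject the null hypothesis if the upper end of the planned two-sided 95% patient-level bootstrap interval is below 1.9; that end is the 97.5% upper limit the test needs. Keep the interval-limited, capped count as a supportive analysis. The bootstrap limit is approximate, so its level should be confirmed by simulation at the planned sample size.

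If the reduced count must carry the decision:

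- stop patient-time at each counted false positive and restart it at the interrogation that closes the interval;
- end patient-time at the second counted false positive for every patient who reaches two;
- state that truncation refers to counted events;
- acknowledge that this restores about 2.5% only if the rate is the same for all patients.

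The cost is a few sentences and modest programming. The preferred change uses an estimator and interval already planned; the fallback uses interrogation dates that the one-per-interval rule already requires. The reported FPR will be somewhat higher and its interval wider. Whether the planned size still gives adequate power cannot be checked from the visible text.
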